# Statistical Analysis Plan

Taisho Pharmaceutical R&D Inc.  
Protocol TS121-US201

Final 2.0  
18 Dec 2018  
CONFIDENTIAL

Statistical Analysis Plan (SAP)

assessment and inventory of symptoms: State versus Trait; Assessability; Face validity; Ecological validity; and Rule of three Ps (pervasive, persistent, and pathological) (SAFER) for confirmation of placebo lead-in eligibility. Results will be communicated to the site prior to Visit 2.

Visit 2 (Start of Placebo Lead-In): Following initial eligibility confirmation, qualified patients will return to the site initiating a 2-week, single-blind placebo lead-in period. An ophthalmologist will conduct a thorough eye examination (including slit lamp under mydriasis). Patients will schedule another phone call for central rater assessments (Visit 2.1), and Visit 3 will be scheduled.

Visit 2.1 (End of Placebo Lead-In): Response to placebo will be assessed using HAM-D by a central rater. The current HAM-D score and change in HAM-D score from Visit 1.1 to Visit 2.1 will be used to determine eligibility.

Visit 3 (Baseline): After completing the placebo lead-in period, patients will return to the site for baseline evaluations. Following confirmation of eligibility, patients will be randomly assigned to receive TS-121 10 mg, 50 mg, or placebo in a 1:1:1 ratio. Patients will be instructed to continue taking investigational product once-daily in the morning and to maintain their current ADT.

Visits 4 (Week 2) and 5 (Week 4): Patients will return to the site for safety and efficacy assessments, dosing compliance, drug accountability and dispensing of a new supply of investigational product. Compliance with the dosing schedule will be assessed. Visit 5 and Visit 6 will be scheduled.

Visit 6 (Week 6): Patients will return to the site for end-of-treatment safety (including ophthalmological examination), efficacy, pharmacokinetic, and exploratory pharmacodynamic assessments and final drug accountability.

End of Treatment (EOT): The EOT visit is Visit 6 for patients who complete treatment and is the last assessment closest to the last treatment day for patients who discontinued from treatment early or failed to complete Visit 6.

Visit 7 (Follow-up): Patients will return to the site for a follow-up evaluation of safety (including ophthalmological examination) and efficacy assessments approximately two weeks after Visit 6.

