# Statistical Analysis Plan

Taisho Pharmaceutical R&D Inc.  
Protocol TS121-US201

Statistical Analysis Plan (SAP)

Final 2.0  
18 Dec 2018  
CONFIDENTIAL

In case an unscheduled clinical laboratory assessment was performed within the visit window for a missing assessment then the unscheduled assessment will be included in the visit summary. In these cases the unscheduled assessment closest to the scheduled time will be used.

Missing data are assumed to be missing at random (MAR).

The primary endpoint for efficacy is Week 6/EOT. Efficacy assessments are not planned to be collected at early termination. The primary analysis will include all available efficacy assessments of the Intent to Treat Population. The primary analysis will use MMRM, in which patients with no post baseline assessment are dropped from the model. A sensitivity analysis will assess the Week 6/EOT of each efficacy endpoint (MADRS total score, CGI, HAM-A total score and SDQ total score) based on a multiple imputation method using all patients with a baseline score, including patients with no post baseline assessment.

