### ***6.3.13.3 Multiple Imputation for Missing Visits***

Multiple imputation method for missing visits will be performed for primary and secondary efficacy endpoints and the summary of treatment differences at Week 6/EOT will be presented as a sensitivity analysis.

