# Statistical Analysis Plan

Taisho Pharmaceutical R&D Inc.  
Protocol TS121-US201

Statistical Analysis Plan (SAP)

Final 2.0  
18 Dec 2018  
CONFIDENTIAL

The following example SAS programming multiple imputation (MI) code will be used to assess pattern of missing visits:

```
Proc MI Nimpute=0;  
    Var GROUP TRT10 TRT50 BASE WEEK2 WEEK4 WEEK6 FOLLOW;  
run;
```

The indicator variables TRT10 (1 for TS-121 10 mg and otherwise 0) and TRT50 (1 for TS-121 10 mg and otherwise 0) are equivalent to the GROUP treatment classification variables.

The following MI code will be used to create a set of imputation data sets.

```
Proc MI Seed=xxxxx Nimpute=x out=impute_1 round= . . . .1 .1 .1 .1 ;  
    EM INITIAL = AC MAXITER=25 CONVERGE=0.00001;  
    Var TRT10 TRT50 BASE WEEK2 WEEK4 WEEK6 FOLLOW;  
run;
```

The number of imputed data sets (Nimpute) will be set to have relative efficiency > 95% for each imputed variable. This number is expected to be < 10.

The MMRM of Section 6.3.13.1 is then run by imputation number to generate two data sets: The model parameters (solutionF, solution for model fixed effects) and the treatment by visit mean differences. Only the set of treatment mean differences used to evaluate the Week 6/EOT treatment mean differences (GROUPDIF1-GROUPDIF2: D50-placebo, D10-placebo, D50-D10) will be sorted by GROUPDIF1, GROUPDIF2 and imputation number.

The following example SAS programming code will be used to evaluate the Week 6/EOT treatment mean differences (D50-placebo, D10-placebo, D50-10):

```
Proc Mianalyze Data=Diff(keep=GROUPDIF1 GROUPDIF2 Est_diff SE_diff) Edf=xx;  
    By GROUPDIF1 GROUPDIF1;  
    Modeleffects Est_diff;  
    Stderr SE_diff;  
    Ods Output Parameterestimates=Est_diff1 VarianceInfo = SE_diff1;  
run;
```

The following example SAS programming code will be used to evaluate the solution for model fixed effects.

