**Table 3**      **Figures to be Included in Section 14 of the Clinical Study Report**

*Note: Top line figures are indicated \**

---

Figure 14.1.1	Patient Disposition (All Screened Patients)  Refer to shells document.
Figure 14.2.1	Plasma ██████████ Concentrations versus Actual Time Post Dose (Pharmacokinetic Population)  Refer to shells document.  Scatter plot using different symbols for TS-121 10 mg and TS-121 50 mg treatment groups. X-axis is actual time post dose.
*Figure 14.2.2.1	Montgomery-Asberg Depression Rating Scale (MADRS) Total Score Treatment Mean (+/- SE) versus Visit (Intent to Treat Population)  Refer to shells document.  Profile plot using different symbols for TS-121 10 mg, TS-121 50 mg and Placebo treatment groups. X-axis in weeks from Baseline through follow-up. Plot Week 6 or ET at 6 weeks and Follow-up at 10 weeks.
*Figure 14.2.2.2	Montgomery-Asberg Depression Rating Scale (MADRS) Total Score Treatment Mean (+/- SE) Change from Baseline versus Visit (Intent to Treat Population)  Refer to shells document.  Profile plot using different symbols for TS-121 10 mg, TS-121 50 mg and Placebo treatment groups. X-axis in weeks from Baseline through follow-up. Plot Week 6 or ET at 6 weeks and Follow-up at 10 weeks. Reference line at zero change from baseline.
Figure 14.2.3.1	Clinical Global Impression Severity (CGI-S) Score Treatment Mean (+/- SE) versus Visit (Intent to Treat Population)  Profile plot using different symbols for TS-121 10 mg, TS-121 50 mg and Placebo treatment groups. X-axis in weeks from Baseline through follow-up. Plot Week 6 or ET at 6 weeks and Follow-up at 10 weeks.
Figure 14.2.3.2	Clinical Global Impression Severity (CGI-S) Score Treatment Mean (+/- SE) Change from Baseline versus Visit (Intent to Treat Population)  Profile plot using different symbols for TS-121 10 mg, TS-121 50 mg and Placebo treatment groups. X-axis in weeks from Baseline through follow-up. Plot Week 6 or ET at 6 weeks and Follow-up at 10 weeks. Reference line at zero change from baseline.
Figure 14.2.4.1	Hamilton Anxiety Scale (HAM-A) Treatment Mean (+/- SE) versus Visit (Intent to Treat Population)  Profile plot using different symbols for TS-121 10 mg, TS-121 50 mg and Placebo treatment groups. X-axis in weeks from Baseline through follow-up. Plot Week 6 or ET at 6 weeks and Follow-up at 10 weeks.

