### Documentation Of Statistical Methods

Appendix 16.1.9.2.1 Statistical Analysis Details of Table 14.2.2.3 and Table 14.2.2.4 Analysis of Montgomery-Asberg Depression Rating Scale (MADRS) Total Score Change from Baseline

Appendix 16.1.9.2.2 Statistical Analysis Details of Table 14.2.2.5 Analysis of Montgomery-Asberg Depression Rating Scale (MADRS) Total Score Change from Baseline at Week 6/EOT

Appendix 16.1.9.2.3 Statistical Analysis Details of Table 14.2.2.6 Montgomery-Asberg Depression Rating Scale (MADRS) Responders Comparison of TS-121 Treatment versus Placebo at Visit 6 (Intent to Treat Population)

Appendix 16.1.9.2.4 Statistical Analysis Details of Table 14.2.3.2 Summary and Analysis of Clinical Global Impression Improvement (CGI-I) Score Frequency, CGI-I Summary Scores and CGI-I Improver Frequency by Treatment and Visit (Intent to Treat Population)

Appendix 16.1.9.2.5 Statistical Analysis Details of Table 14.2.3.3 and Table 14.2.3.4 Analysis of Clinical Global Impression Severity (CGI-S) Score Change from Baseline (Intent to Treat Population)

Appendix 16.1.9.2.6 Statistical Analysis Details of Table 14.2.4.2 and Table 14.2.4.3 Analysis of Hamilton Anxiety Scale (HAM-A) Change from Baseline (Intent to Treat Population)

Appendix 16.1.9.2.7 Statistical Analysis Details of Table 14.2.5.3 and Table 14.2.5.4 Analysis of Symptoms of Depression Questionnaire (SDQ) Total Score Change from Baseline (Intent to Treat Population)

Appendix 16.1.9.2.8 Statistical Analysis Details of Table 14.2.7.2 Analysis of Inflammatory Markers Change from Baseline at Visit 6 (Intent to Treat Population)

Appendix 16.1.9.2.9 Multiple Imputation Method for Missing Visits Statistical Analysis Details of Table 14.2.2.3.1 and Table 14.2.2.4.1 Analysis of Montgomery-Asberg Depression Rating Scale (MADRS) Total Score Change from Baseline

Appendix 16.1.9.2.10 Multiple Imputation Method for Missing Visits Statistical Analysis Details of Table 14.2.2.5.1 Analysis of Montgomery-Asberg Depression Rating Scale (MADRS) Total Score Change from Baseline at Week 6/EOT

Appendix 16.1.9.2.11 Multiple Imputation Method for Missing Visits Statistical Analysis Details of Table 14.2.2.6.1 Montgomery-Asberg Depression Rating Scale (MADRS) Responders Comparison of TS-121 Treatment versus Placebo at Visit 6 (Intent to Treat Population)

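### The only labelled missing-data sensitivity analysis makes the same MAR assumption as the primary MMRM, so their agreement cannot speak to informative dropout; its rule for the number of imputations also leaves a borderline p-value dependent on the seed

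*SAP*

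**What the plan says.** SAP 6.3.4 assumes MAR, makes the MMRM primary, and names multiple imputation, extended to patients with no post-baseline score, as the sensitivity analysis. It adds: "Efficacy assessments are not planned to be collected at early termination". The visit schedule agrees, with no MADRS in the early-termination columns.

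SAP 6.3.13.3 imputes missing visits from treatment indicators, baseline and visit scores, reruns the 6.3.13.1 MMRM on each completed data set and pools; "the summary of treatment differences at Week 6/EOT will be presented as a sensitivity analysis". On the number of imputations: "The number of imputed data sets (Nimpute) will be set to have relative efficiency > 95% for each imputed variable", followed by "This number is expected to be < 10". The seed in the example code is a placeholder. SAP Table 4 lists eight imputation appendices (16.1.9.2.9 to 16.1.9.2.16), all under one method name, for example "Multiple Imputation Method for Missing Visits Statistical Analysis Details of Table 14.2.2.3.1 and Table 14.2.2.4.1". No delta-adjusted or reference-based run appears.

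On Week 6/EOT, SAP section 1 says that EOT "is the last assessment closest to the last treatment day for patients who discontinued from treatment early or failed to complete Visit 6", and the MADRS figure specification in SAP Table 3 says "Plot Week 6 or ET at 6 weeks and Follow-up at 10 weeks". SAP 6.3.4 and the separate `WEEK6` variable in 6.3.13.3 point instead to a missing cell for dropouts.

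**The concern.** A sensitivity analysis should vary the assumption most open to doubt. Here that assumption is MAR. Protocol 8.5 and 11.4 link a poor CGI-I score to evaluation for discontinuation, and no efficacy assessment is planned at the early-termination visit, so worsening between the last scheduled visit and withdrawal may go unmeasured. The planned imputation tests some modelling choices and adds patients without post-baseline data, but it keeps MAR.

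Both documents call this a pilot whose results will be used to estimate the effect size for future studies, so the size of the Week 6 difference matters even without a confirmatory claim. A reader who sees MMRM and imputation agree could wrongly take that as evidence that dropout did no harm.

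Two further points affect how the analysis is read. With few imputations and no fixed seed, a sensitivity p-value near 0.05 can fall on either side of it. And the two readings of Week 6/EOT give different estimates.

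**Working it through.** **Inputs.** From the documents: about 180 randomized 1:1:1, so about 60 per arm; two-sided 5% level; relative efficiency above 95%; fewer than 10 imputations expected. Assumed, because the documents give none: 10/20/30% of Week 6 scores missing; missing-information fraction λ of 0.1/0.2/0.3; MADRS SD 9; correlation 0.6; effect -3 to -5 points.

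**1. The plan's own figure.** Relative efficiency is 1/(1 + λ/m). Requiring more than 0.95 gives m > 19λ, that is m > 1.9, 3.8 and 5.7, so the smallest m is 2, 4 and 6. The expectation of fewer than 10 is reproduced for any λ below 9/19 = 0.474.

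**2. Can imputation reveal departures from MAR?** In simulated trials with 60 per arm, an effect of -3 under MAR and 20% dropout, TS-121 dropouts' unobserved scores were made worse by 0, 4 or 8 points. The true effect including dropouts was then -3.0, -2.2 or -1.4. Maximum likelihood (as in the MMRM) and imputation both gave -2.97 in all three cases. Neither can respond to a shift in scores it never sees.

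**3. Size of a departure.** If a fraction f of TS-121 Week 6 scores is missing and worse by δ than MAR predicts, with no shift on placebo, the difference moves by f × δ. For an effect read as -4, the sample-size ratio for the next trial is (4/(4 - fδ))².

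| f | shift, δ=2 | ratio | shift, δ=5 | ratio |
|---|---|---|---|---|
| 10% | 0.2 | 1.11 | 0.5 | 1.31 |
| 20% | 0.4 | 1.23 | 1.0 | 1.78 |
| 30% | 0.6 | 1.38 | 1.5 | 2.56 |

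**4. Tipping δ.** Trials of 3 × 60 were simulated with 20 MAR imputations, adding δ to the imputed Week 6 scores of TS-121 dropouts. The δ at which the 95% interval first includes 0 solves estimate + fδ + t × SE(δ) = 0. SE at δ = 0 was 1.38/1.45/1.55 for 10/20/30% missing.

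| MAR estimate | 10% | 20% | 30% |
|---|---|---|---|
| -3.5 | 6.9 | 3.0 | 1.3 |
| -4 | 10.9 | 5.3 | 2.9 |
| -5 | 18.1 | 9.5 | 6.0 |

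**5. Dependence on the seed.** The efficiency rule requires only λ/m < 1/19, so Monte Carlo error can reach √(1/19) = 0.23 of the standard error. P-values were simulated by Rubin pooling with Barnard-Rubin degrees of freedom (complete-data df 150 assumed; 400,000 draws per cell). With a converged p of 0.05, the central 90% of seeds gives:

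| λ | smallest m | m = 9 | m = 100 |
|---|---|---|---|
| 0.1 | 0.019-0.173 (m=2) | 0.033-0.079 | 0.044-0.057 |
| 0.2 | 0.018-0.153 (m=4) | 0.026-0.101 | 0.041-0.061 |
| 0.3 | 0.017-0.153 (m=6) | 0.021-0.124 | 0.039-0.065 |

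Across all trials, not only borderline ones, the verdict at 0.05 differs from the converged one in about 3% (no effect) and 9-10% (effect -4) at the smallest m, 1-2% and 3-7% at m = 9, and at most 0.6% and 1.9% at m = 100.

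**6. The two readings of Week 6/EOT.** Suppose the effect builds as -1.33, -2.67, -4 at Weeks 2, 4, 6, dropout is ignorable and spread evenly before the three visits, and patients with no post-baseline score leave the MMRM. Filling the cell with the last assessment gives [(1-f)(-4) + (f/3)(-1.33) + (f/3)(-2.67)]/(1 - f/3) = -3.86/-3.71/-3.56 at f = 10/20/30%, against -4.00 if the cell stays missing. Only f/3, or 3/7/10%, of Week 6 scores would then be imputed.

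**7. Code in 6.3.13.3.** `TRT50` is defined as 1 for TS-121 10 mg, the same as `TRT10`, although the text says the two indicators are equivalent to the three-level group variable. The `BY` statement names `GROUPDIF1` twice, although the data are sorted by `GROUPDIF1` and `GROUPDIF2`. Run as printed, the imputation model would have no 50 mg indicator and contrasts sharing `GROUPDIF1` would be pooled. Both look like typing errors.

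**The case against.** The strongest objection is that the plan does contain one analysis that treats dropouts differently. The ANCOVA on the latest assessment (SAP 6.3.13.1) uses each patient's last observed change, may include patients with no post-baseline data, and lets the treatment difference vary with time on treatment. It is a top-line table. The plan also examines the pattern of missing visits and tabulates withdrawal reasons by arm. This stands in part: not everything that touches dropout relies on MAR. But the ANCOVA is presented as an assessment of time on treatment, states no departure from MAR, and gives no indication of how large a departure would change the conclusion.

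On the seed, the efficiency rule is a floor and fewer than 10 is an expectation, so 100 imputations would already comply. The rule covers every imputed variable, so the follow-up visit may force a larger m than Week 6 alone: with λ = 0.2 at Week 6 and 0.3 at follow-up, m is 6, the range narrows to 0.022-0.121, and discordance at effect -4 falls to 6.3%. Few imputations do not inflate false positives (rejection under no effect stays near 0.048), and at effect -4 most discordant verdicts lose significance. The sensitivity p-value has no decision rule. All this stands, and makes the seed the lesser point.

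The shift in step 3 is one-sided: an equal shift in all arms at equal dropout cancels. Neither document says whether the effect should include outcomes after dropout. If the last assessment fills Week 6/EOT, less is imputed and the figures in steps 3 and 4 would shrink. Some tipping values are also reassuringly large.

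**Conclusion.** The concern holds. Agreement between the MMRM and the planned imputation gives no information about informative dropout, whatever the dropout rate. The possible effect is f × δ: 0.2 to 1.5 MADRS points over 10-30% missing and δ of 2 to 5, if only TS-121 dropouts are affected and the effect is meant to include their outcomes. These are conditional illustrations, not expected errors.

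The seed problem is real but confined to a supportive p-value. The Week 6/EOT ambiguity moves an effect of -4 by 0.14 to 0.44 points under the assumptions in step 6, and it touches the definition of the primary endpoint. The MMRM remains a reasonable primary analysis. The change should be made, but the trial's validity does not depend on it.

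**What to change.** - Keep the MMRM as primary and the MAR imputation as a check on the model.
- Add a tipping-point analysis over a stated range of δ, or a placebo-reference imputation, for Week 6 MADRS in TS-121 dropouts. If the MAR interval excludes 0, report the δ at which the Week 6 interval first includes it.
- State one rule for Week 6/EOT: either the last assessment fills the cell, or `WEEK6` stays missing for dropouts in both the MMRM and the imputation. Reconcile SAP section 1, 6.3.4, 6.3.13.1, 6.3.13.3 and Table 3 accordingly.
- Pre-specify the seed and a large number of imputations, for example 100.
- Define `TRT50` as 1 for TS-121 50 mg and correct the `BY` statement to `GROUPDIF1 GROUPDIF2`.

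The cost is SAP text, one data step between the imputation and the MMRM refit, and run time. No new data are needed. The added estimate may be less favourable to TS-121.

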# Statistical Analysis Plan

Taisho Pharmaceutical R&D Inc.  
Protocol TS121-US201

Statistical Analysis Plan (SAP)

Final 2.0  
18 Dec 2018  
CONFIDENTIAL

```
Proc Mianalyze Parm(sclassvar=full)= solutionF;  
    Class GROUPDIF TIME;  
    Modeleffects BASE GROUP TIME GROUP*TIME;  
run;
```

The sensitivity analysis for MADRS treatment mean differences at Week 6/EOT will be presented [Table 14.2.2.3.1] and the MI analysis for MMRM fixed effects will be reported separately [Table 14.2.2.4.1]. Details of the MI analysis will be presented in a statistical appendix.

Supplementary summary tables and statistical appendices will also be presented for the MI analysis for MMRM fit to secondary endpoints.

## 6.3.14 Pharmacodynamic (PD) Analysis

All results, including baseline PD biomarkers (salivary cortisol, hair cortisol, plasma copeptin, 8h urinary cortisol) and inflammatory markers (IL-1, IL-6, HS-CRP, and TNF- $\alpha$ ), will be listed with relevant metadata, as, for example, urine volume and concentration used to calculate 8h urinary cortisol.

### 6.3.14.1 Plasma Copeptin

Plasma copeptin and change from baseline will be presented in a listing [Listing 16.2.6.5] and summarized [Table 14.2.6.1]. Change from baseline to Visit 6 will be compared between TS-121 treatments and placebo using an analysis of covariance. The following is example SAS programming code that will be used to fit the model and evaluate treatment mean differences:

```
Proc Mixed Method = REML;  
    Class GROUP Subject_ID;  
    Model Change = Baseline GROUP baseline*GROUP / ddfm=kenwardroger;  
    Random subject_ID;  
    lsmeans GROUP / pdiff alpha=0.05 cl;  
    ods output lsmeans=lsm diffs=diffs;  
run; quit;
```

Least squares mean differences with 95% confidence intervals for TS-121 10 mg versus placebo and for TS-121 50 mg versus placebo evaluated at Visit 6 will be presented [Table 14.2.6.2].

# Statistical Analysis Plan

Taisho Pharmaceutical R&D Inc.  
Protocol TS121-US201

Statistical Analysis Plan (SAP)

Final 2.0  
18 Dec 2018  
CONFIDENTIAL

Statistical significance of the baseline\*Group interaction will be noted. In case this has  $p < 0.1$  then the distribution of baseline plasma copeptin across treatment groups will be examined and a different model for comparing plasma copeptin change from baseline across treatment groups may be assessed.

The association between baseline plasma copeptin and baseline MADRS total score will be presented in a scatter plot of MADRS baseline total score versus baseline plasma copeptin [Figure 14.2.6.1.1] for the intent to treat population. The association between biomarker response to treatment and treatment efficacy will be presented in a scatter plot of MADRS total score change from baseline versus plasma copeptin change from baseline [Figure 14.2.6.1.2] for the intent to treat population.

### **6.3.14.2 Inflammatory Markers**

Inflammatory markers (IL-1, IL-6, HS-CRP, and TNF- $\alpha$ ) and change from baseline will be presented in a listing [Listing 16.2.6.6] and summarized [Table 14.2.7.1]. Change from baseline at Visit 6 will be compared between TS-121 treatments and placebo using an analysis of covariance for change dependent on baseline, treatment and baseline by treatment interaction. Least squares mean differences with 95% confidence intervals for TS-121 10 mg versus placebo and for TS-121 50 mg versus placebo evaluated at Visit 6 [Table 14.2.7.2].

The association between inflammatory markers at baseline and baseline MADRS total score will be presented in separate scatter plots of MADRS baseline total score versus each inflammatory marker for the intent to treat population [Figure 14.2.6.2.1]. The association between biomarker response to treatment and treatment efficacy will be presented in separate scatter plots of MADRS total score change from baseline versus each inflammatory marker change from baseline [Figure 14.2.6.2.2] for the intent to treat population.

